5.9.6. Main Treatment Lines Received Over the Entire Follow-up Period

For each main treatment line, the number of main treatment lines, the nature of treatments, the duration and reasons for discontinuation will be presented over the entire follow-up (retrospective phase and prospective phase) overall and based on the current treatment at inclusion (targeted therapy/ chemotherapy / somatostatin analog).

The number of main treatment lines received during the study (quantitative and by class), the nature of lines of treatment received during the study (other than those received at inclusion) and the total number of treatment lines received will be shown based on the "at least one targeted therapy before inclusion (yes /no)" subgroup.

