2.4 History of the illness Initial diagnosis of pancre Date of diagnosis: Tumour at diagnosis: Previous local and/or reg During the course of the dis NK If yes, Surgery Radiofr Chemo Other, Most recent examination Octreoscan, Octreoscan, Octreoscan,	status at enrolment:
2.4 History of the illness Initial diagnosis of pancre Date of diagnosis: Tumour at diagnosis: Previous local and/or reg During the course of the dis NK If yes, Surgery Radiofr Chemo Other, Most recent examination Octreoscan, Octreoscan, Octreoscan, PET scan	eatic neuroendocrine tumour
2.4 History of the illness Initial diagnosis of pancro Date of diagnosis: Tumour at diagnosis: Previous local and/or reg During the course of the dis NK If yes, Surgery Radiofr Chemo Chemo Other, Most recent examinatior Octreoscan, Octreoscan, Octreoscan, PET scan Yes F	status at enrolment:

Observational study protocol final version of 17/07/2018

Ki67	Value obtained	□ Yes	□No	if yes, Ki67 value: % or □ NK
Mitotic index	Value obtained	☐ Yes	□ No	
if yes, mitotic in	dex value: mit	oses/field	d or □ 1	NK
French NET path	ology network 2n	d opinion	ı □ Yes	□ No □ Not known

History of previous tumour-directed systemic treatments

Please describe all previous treatment lines:

Table 1 - Previous tumour-dire	cted cancer treatm	nents		
Name	Treatment line	Combined with	Duration	Reason for stopping
		somatostatin		
		analogues		
Chemotherapy:	☐ First line	☐ Yes ☐ No	(eCRF display:	☐ Adverse event*
□ 5 FU	☐ Second line	□ Octreotide□ Lanreotide	Duration	☐ Progression
☐ Capecitabine (Xeloda®)	☐ Third line	Lameotide	recorded	☐ Scheduled treatment
☐ Doxorubicin (Adriamycin®)			only if the	discontinuation
☐ Streptozocin (Zanosar®)			treatment is a TT)	☐ Patient decision
☐ Temolozomide (Temodal®)			a 11)	
☐ Dacarbazine (Deticene®)			1.1	
Oxaliplatin (Eloxatin®)			months	☐ Other, please state:
☐ Gemcitabine (Gemzar®)				
☐ Cisplatin				□NK
□ VP-16				
☐ Other, please state:				
☐ Interferon Alpha				
a interieron Alpha				
Targeted therapies				
☐ Everolimus				
☐ Sunitinib				
Somatostatin analogues				
☐ Octreotide				
☐ Lanreotide				
☐ Radionuclide therapy				
Other place states				
Other, please state:				

^{*} In the event of an AE related to a Pfizer product, please complete the safety section of the CRF (lines may be added if there have been more treatments, up to a limit of 3 previous lines)

RADIONUCLIDE THERAPY screen - Treatment initiation

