Number of patient receiving a main treatment at least once during the study $(N(\%))$:	XX (XX.X%)	XX (XX.X%)	XX (XX.X%)
- Targeted therapy - Everolimus	XX (XX.X%) XX (XX.X%)	XX (XX.X%) XX (XX.X%)	XX (XX.X%) XX (XX.X%)
- Sunitinib	XX (XX.X%)	XX (XX.X%)	XX (XX.X%)
- Other treatment	XX (XX.X%)	XX (XX.X%)	XX (XX.X%)
- Chemotherapy	XX (XX.X%)	XX (XX.X%)	XX (XX.X%)
- Somatostatin analog	XX (XX.X%)	XX (XX.X%)	XX (XX.X%)
- Metabolic radiotherapy	XX (XX.X%)	XX (XX.X%)	XX (XX.X%)
- Interferon alpha	XX (XX.X%)	XX (XX.X%)	XX (XX.X%)
- Other	XX (XX.X%)	XX (XX.X%)	XX (XX.X%)
Number of patients receiving at least one main treatment and/or a combination during the study (N(%)):	XX (XX.X%)	XX (XX.X%)	XX (XX.X%)
- Targeted therapy	XX (XX.X%)	XX (XX.X%)	XX (XX.X%)
- Everolimus	XX (XX.X%)	XX (XX.X%)	XX (XX.X%)
- Sunitinib	XX (XX.X%)	XX (XX.X%)	XX (XX.X%)
- Other treatment	XX (XX.X%)	XX (XX.X%)	XX (XX.X%)

^{*} In the case of previous treatment, the length of the targeted therapies is to be taken directly from the e-CRF (data not calculated).

Table 14.2.2.2.12: Treatments Received at Least Once During the Study According to the Treatment at Inclusion – Reference Set

	Targeted therapies (N=XX)	Other treatments (N=XX)	Total (N=XX)
- Chemotherapy	XX (XX.X%)	XX (XX.X%)	XX (XX.X%)
- Somatostatin analog	XX (XX.X%)	XX (XX.X%)	XX (XX.X%)
- Metabolic radiotherapy	XX (XX.X%)	XX (XX.X%)	XX (XX.X%)
- Interferon alpha	XX (XX.X%)	XX (XX.X%)	XX (XX.X%)
- Other	XX (XX.X%)	XX (XX.X%)	XX (XX.X%)
Number of patients receiving at least once during the study:			
Treatment XX alone	XX (XX.X%)	XX (XX.X%)	XX (XX.X%)
Combination 1	XX (XX.X%)	XX (XX.X%)	XX (XX.X%)
Combination 2	XX (XX.X%)	XX (XX.X%)	XX (XX.X%)

Using the same template:

Table 14.2.2.2.13: Treatments Received at Least Once During the Study According to Treatment at Inclusion – Safety Analysis Set

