9.3.5. Treatment Lines Received Throughout the Follow-up

Table 14.2.2.5.1: Treatment Lines Received Throughout the Follow-Up Based on Treatment Groups at Inclusion – Reference Set

		Targeted therapies (N=XX)	Other (N=XX)	Total (N=XX)
Number of main treatment lines by patient	N	XX	XX	XX
	Missing data 1 2	XX XX (XX.X%) XX (XX.X%) XX (XX.X%)	XX XX (XX.X%) XX (XX.X%) XX (XX.X%)	XX XX (XX.X%) XX (XX.X%) XX (XX.X%)
Patients with at least one main line of treatment per site	N	XX	XX	XX
of treatment per site	Missing data First main line of treatment Second main line of treatment	XX XX (XX.X%) XX (XX.X%) XX (XX.X%)	XX XX (XX.X%) XX (XX.X%) XX (XX.X%)	XX XX (XX.X%) XX (XX.X%) XX (XX.X%)
Patients with at least one main line of treatment by type of treatment (1)	N	XX	XX	XX
of deadless by type of deadless (1)	Missing data Targeted therapies >> Everolimus >> Sunitinib Chemotherapy Somatostatin analogs Interferon alpha Metabolic radiotherapy Other treatment >>	XX XX (XX.X%) XX (XX.X%) XX (XX.X%) XX (XX.X%) XX (XX.X%) XX (XX.X%) XX (XX.X%) XX (XX.X%) XX (XX.X%)	XX XX (XX.X%) XX (XX.X%) XX (XX.X%) XX (XX.X%) XX (XX.X%) XX (XX.X%) XX (XX.X%) XX (XX.X%)	XX XX (XX.X%) XX (XX.X%) XX (XX.X%) XX (XX.X%) XX (XX.X%) XX (XX.X%) XX (XX.X%) XX (XX.X%) XX (XX.X%)
First main line of treatment (1)	N Missing data Targeted therapies >> Everolimus >> Sunitinib Chemotherapy Somatostatin analogs Interferon alpha Metabolic radiotherapy Other treatment	XX XX XX (XX.X%) XX (XX.X%) XX (XX.X%) XX (XX.X%) XX (XX.X%) XX (XX.X%) XX (XX.X%)	XX XX XX (XX.X%) XX (XX.X%) XX (XX.X%) XX (XX.X%) XX (XX.X%) XX (XX.X%) XX (XX.X%)	XX XX XX (XX.X%) XX (XX.X%) XX (XX.X%) XX (XX.X%) XX (XX.X%) XX (XX.X%) XX (XX.X%)
Combination with this line of treatment (1)	N	XX	XX	XX
	Missing data Treatment 1 Treatment N	XX XX (XX.X%) XX (XX.X%) XX (XX.X%)	XX XX (XX.X%) XX (XX.X%) XX (XX.X%)	XX XX (XX.X%) XX (XX.X%) XX (XX.X%)
Duration of first main line of treatment (months) (1)(2)	N	XX (XX.X%)	XX (XX.X%)	XX (XX.X%)
	Missing data	XX	XX	XX
	Mean (SD)	XX.XX (X.XX)	XX.XX (X.XX)	XX.XX (X.XX)
	Mean [Min; Max] [Q1; Q3]	XX.X [XX.X; XX.X] [XX.X; XX.X]	XX.X [XX.X; XX.X] [XX.X; XX.X]	XX.X [XX.X; XX.X] [XX.X; XX.X]

Table 14.2.2.5.1: Treatment Lines Received Throughout the Follow-Up Based on Treatment Groups at Inclusion – Reference Set

		Targeted therapies (N=XX)	Other (N=XX)	Total (N=XX)
Reason for discontinuation – First main line of treatment (1)	N	XX	XX	XX
	Missing data	XX	XX	XX
	Adverse event	XX (XX.X%)	XX (XX.X%)	XX (XX.X%)

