	Progression	XX (XX.X%)	XX (XX.X%)	XX (XX.X%)
	Planned discontinuation of treatment	XX (XX.X%)	XX (XX.X%)	XX (XX.X%)
	Patient decision	XX (XX.X%)	XX (XX.X%)	XX (XX.X%)
	Other	XX (XX.X%)	XX (XX.X%)	XX (XX.X%)
Reason for discontinuation (0) –				
First main line of treatment by type of treatment (1)	N	XX	XX	XX
,	Missing data	XX	XX	XX
	Targeted therapies	XX (XX.X%)	XX (XX.X%)	XX (XX.X%)
	>> Adverse event	XX (XX.X%)	XX (XX.X%)	XX (XX.X%)
	>> Progression	XX (XX.X%)	XX (XX.X%)	XX (XX.X%)
	>> Planned discontinuation of treatment	XX (XX.X%)	XX (XX.X%)	XX (XX.X%)
	>> Patient decision	XX (XX.X%)	XX (XX.X%)	XX (XX.X%)
	>> Other	XX (XX.X%)	XX (XX.X%)	XX (XX.X%)
Second main line of treatment (1)	 N	XX	XX	XX
	Missing data	XX	XX	XX
	Targeted therapies	XX (XX.X%)	XX (XX.X%)	XX (XX.X%)
	>> Everolimus	XX (XX.X%)	XX (XX.X%)	XX (XX.X%)

(0) Percentages calculated as a proportion of the number of patients in the treatment class concerned.

Programmer notes:

- For the variable "Lines of treatment" show the frequencies for all previous lines of treatment received by patients: line 1 ... line N.
- Also show the duration (if targeted therapy) and reason for discontinuing the lines of treatment.
- N treatments describe the combination with somatostatin analogs.
- Group together all chemotherapies (combinations of chemotherapies included) under the title 'Chemotherapy'.
- Group together Lanreotide and Octreotide under somatostatin analogs for all of the analyses in this table and sunitinib and Everolimus under the targeted therapies in the analyses of treatment combinations by line of treatment and overall treatment regimen.

Using the same template:

Table 14.2.2.5.2: Main Treatment Lines Received Throughout the Follow-Up Based on Treatment Groups at Inclusion – Reference Set – Treatment Subgroup Analysis

⁽¹⁾ Percentages calculated as a proportion of patients concerned.

⁽²⁾ Not available for the duration of previous treatments other than targeted therapies.

Table 14.2.2.5.3: Main Treatment Lines Received Throughout the Follow-Up – Reference Set – Subgroup Analysis Based on at Least One Targeted Therapy before Inclusion (Yes/No)

		At least one targeted therapy received before inclusion (N=XX)	No targeted therapy received before inclusion (N=XX)	Total (N=XX)
Number of main treatment lines received				
during the study	N	XX	XX	XX
	Missing data	XX	XX XX.XX	XX
	Mean (SD)	XX.XX(X.XX)	(X.XX)	XX.XX (X.XX)

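### Line durations pooled over both phases by treatment at inclusion leave out every non-targeted line that ended before inclusion but keep the targeted-therapy ones

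*SAP*

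**What the plan says.** **Reporting rule.** SAP 5.9.6 states that, for each main line, "the duration and reasons for discontinuation will be presented over the entire follow-up (retrospective phase and prospective phase"). The presentation is "overall and based on the current treatment at inclusion (targeted therapy/ chemotherapy / somatostatin analog").

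**Table shell.** SAP 9.3.5 implements this in Table 14.2.2.5.1, titled "Treatment Lines Received Throughout the Follow-Up Based on Treatment Groups at Inclusion", with columns for targeted therapies, other treatments and total. The row is "Duration of first main line of treatment (months) (1)(2"). It is not split by the drug given in that line. Table 14.2.2.5.2 repeats the template by treatment subgroup.

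**Data collected.** The CRF appended to the protocol lists previous tumour-directed treatments in section 2.4, Table 1. Its duration cell is displayed only if the "treatment is a TT", that is, a targeted therapy. The table has no start or stop dates. Protocol 9.2 and SAP 6.2 agree that for earlier lines only their number and regimens are otherwise collected. A programmer note in SAP 9.3.1 adds: "In the case of previous treatment, the length of the targeted therapies is to be taken directly from the e-CRF (data not calculated").

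**What the SAP says about the gap.** Footnote (2) to the duration row reads "Not available for the duration of previous treatments other than targeted therapies". A programmer note to the same table reads "Also show the duration (if targeted therapy) and reason for discontinuing the lines of treatment".

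**The concern.** The row label promises the duration of first-line treatment in each group. The data cannot supply it for anyone included on line 2 or later whose first line was not a targeted therapy. Whether a duration is present depends on the drug and on whether the line had ended before inclusion, so the missing values are not a random subset.

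The two columns are also affected differently. Under other treatments, the row combines non-targeted lines held at inclusion by first-line patients with earlier targeted-therapy lines of later-line patients. Under targeted therapies, every known first-line duration is a targeted-therapy duration, because line-1 patients are on such a drug and earlier lines have a duration only if they were one. A reader comparing the columns would be comparing differently selected sets of lines.

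Describing patient management is a stated secondary objective, so the row bears on a question that the study is meant to answer.

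**Working it through.** The plan gives no figure to reproduce. The check has two parts.

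**1. Can an earlier targeted therapy occur in the other-treatments column?** Yes. Protocol 5.1.2, the CRF and SAP 3.3 exclude only patients receiving a targeted therapy that they have already had. SAP 5.9.1 defines a subgroup by targeted therapy before inclusion. The protocol summary words the exclusion more broadly. Under that wording no earlier targeted therapy would enter the column, but the earlier non-targeted durations would still be missing.

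**2. Illustration for the first-line row, other-treatments column.**

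Inputs:
- N = 75, the maximum for this group in Protocol 5.1 and SAP 3.3. It cancels from the percentages.
- a = share included on line 1: assumed 30% to 50%.
- g = share of later-line patients whose first line was a targeted therapy: assumed 10% to 30%.

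The documents give neither a nor g.

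Formulas:
- Durations known = N × [a + (1 − a)g]
- Targeted share of known values = (1 − a)g / [a + (1 − a)g]
- Targeted share if every duration had been recorded = (1 − a)g

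| a | g | Known durations | Known, % | Targeted, % of known | Targeted, % if all recorded |
|---|---|---|---|---|---|
| 30% | 10% | 22.5 + 5.25 = 27.75 | 37% | 5.25/27.75 = 19% | 5.25/75 = 7% |
| 30% | 30% | 22.5 + 15.75 = 38.25 | 51% | 15.75/38.25 = 41% | 15.75/75 = 21% |
| 50% | 10% | 37.5 + 3.75 = 41.25 | 55% | 3.75/41.25 = 9% | 3.75/75 = 5% |
| 50% | 30% | 37.5 + 11.25 = 48.75 | 65% | 11.25/48.75 = 23% | 11.25/75 = 15% |

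The counts are expected values, so fractions are harmless. Over this grid, 35% to 63% of first-line durations are missing, all of them from earlier non-targeted lines. Column definition alone would put 5% to 21% targeted-therapy values in the row; the recording gap raises this to 9% to 41%.

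The rows for later lines follow the same logic for patients included beyond the line in question, but they also contain lines started after inclusion, whose dates are recorded for all drugs.

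**The case against.** **The gap is disclosed.** Footnote (2) is attached to the duration row, the row prints the number missing, and neighbouring rows give first-line treatment by type and discontinuation reasons by type. This stands: nothing is hidden. The footnote does not, however, say that the remaining values are selected by drug, and it does not separate them.

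**Mixing follows from the column definition.** A reader might infer that the recording gap puts targeted-therapy durations into the other-treatments column. It does not. Columns follow treatment at inclusion and rows follow line number, so mixing would occur with complete data. The gap changes its composition.

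**Short lines are not all lost.** A reader might infer that, outside targeted therapy, only lines already running at inclusion count. The documents do not support this. Incident patients start treatment at or after inclusion and contribute short lines in full, as do lines started later. What is missing is non-targeted lines that ended before inclusion, whatever their length.

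**Class-specific durations are planned elsewhere.** SAP 5.9.3 and Tables 14.2.2.2.1.5 to 14.2.2.2.1.7 cover targeted therapy before and after inclusion. SAP 5.7.1 and Tables 14.3.1.1 to 14.3.1.4 give exposure by treatment. This stands, and it lowers the importance of the point.

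**The programmer note may not conflict.** Read literally, it would leave only targeted-therapy durations in the table. But the note just before it speaks of previous lines, and a near-identical note belongs to the previous-line tables. Confined to previous lines, it agrees with footnote (2). It is ambiguous, not clearly a separate rule.

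**Conclusion.** The point holds at minor severity. As written, the duration rows of Tables 14.2.2.5.1 and 14.2.2.5.2 summarise a drug-selected set of lines, and the footnote discloses this without repairing it. That conclusion rests on the CRF field and the table shells, not on the illustration.

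The size is uncertain. The 37% to 65% known and the 9% to 41% targeted share depend on assumed line and treatment distributions that the documents do not give.

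Two wider inferences are not supported. The primary results are not touched: the rows are descriptive, carry no test, and do not feed progression-free survival, overall survival or safety. SAP 5.9.7 already excludes earlier lines from per-line progression-free survival because the information is insufficient. Nor does the problem extend to Table 14.2.2.5.3, whose shell has no duration row.

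**What to change.** In SAP 5.9.6 and Tables 14.2.2.5.1 and 14.2.2.5.2:

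- Report duration by the class of the line itself, as the shell already does for discontinuation reasons.
- For chemotherapy, somatostatin analogues, interferon and radionuclide therapy, restrict duration to lines ongoing at or started after inclusion, following SAP 5.9.7.
- For targeted therapy, show durations before and after inclusion separately, or cross-refer to Tables 14.2.2.2.1.5 to 14.2.2.2.1.7.
- Drop the pooled duration row, and reword the programmer note so that it states one rule. Table 14.1.4.1.10 gives a model: its duration row is labelled as applying only to targeted therapy.

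Table 14.2.2.5.3 needs no change. The cost is SAP wording and re-cut rows; no new data are required.

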5.9.7. Progression-free Survival

Progression-free survival of treatment received at inclusion will be estimated based on the following subgroups:

- At least one targeted therapy before inclusion (yes/no).
- At least one targeted therapy at any time (yes/no).
- Patients receiving chemotherapy as main 2nd line treatment vs patients receiving targeted therapy as main 2nd line treatment.
- Ki67 (≤10%, >10%).
- At least two targeted therapies vs one targeted therapy before inclusion (yes/no).
- At least two targeted therapies vs one targeted therapy at any time of the study (yes/no).
- At least a 1st targeted therapy as line 1 or 2 vs at least a 1st targeted therapy as line 3 or 4 at any time during the study.
- Stage at diagnosis (localised /metastatic).
- At least one surgery at any time of the study (yes/no).
- For 1st line patients at inclusion:
 - Based on targeted therapy/chemotherapy/somatostatin analog at inclusion;
 - At least one targeted therapy at any time of the study (yes/no).
- For 2nd line patients at inclusion:
 - Based on targeted therapy/chemotherapy/somatostatin analog (main treatment) at inclusion;
 - At least one targeted therapy before inclusion (yes/no);
 - At least one targeted therapy at any time of the study (yes/no).
- For metasynchronous patients:
 - Based on current main treatment at inclusion (targeted therapy/ chemotherapy / somatostatin analog);
 - Based on the 1st targeted therapy line at any time of the study (targeted therapy as line 1 or 2, targeted therapy as line 3 or 4).

- For chemotherapy patients at inclusion:
 - Based on line number at inclusion ($\leq 2, \geq 2$);
 - Based on the total number of main treatment lines over the entire follow-up $(\le 2, >2)$.

Progression-free survival will also be estimated overall for patients receiving targeted therapy at any time of the study based on:

- Liver invasion ($\leq 50\%$, $\geq 50\%$);
- Number of metastatic sites ($\leq 2, \geq 2$).

Analyses of progression-free survival will also be conducted on patient subgroups by main treatment line and by main treatment. These analyses will be calculated from the start of each line (ie, the baseline date will be the start date of the main treatment of any new line after changing the main treatment). Therefore, patients may appear as many times as they have changed their main treatment. Only the lines at inclusion and subsequently will be considered in these analyses, as the information collected for previous lines is not sufficient for a survival analysis. Progression-free survival according to the main treatment lines will not be shown if the start date of the main treatment is later than the date of the last visit. In addition, for this analysis, patients will be censored based on the date of the last tumour assessment or clinical assessment for the line, when patients change line without reporting a progression. When there is no date for the tumour or clinical assessment, patients will be censored on the date they discontinued treatment in relation to the line being analysed.

Progression-free survival by subgroup will be analysed using the method described for analysing progression-free survival in the main analysis, which uses as the baseline date the date of starting the main treatment at inclusion (see above). The Kaplan-Meier method, with right censoring and left truncation, uses the PROC PHREG SAS® procedure.

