5.9.8. Overall Survival

In order to better describe the NET patients regardless of their therapeutic management, overall survival will be estimated for all patients, firstly from the time of diagnosis (baseline date = date of diagnosis) and secondly for patients included in the first line of treatment (baseline date = date of 1st line treatment was started if available).

In addition, overall survival (baseline date = date of diagnosis) will also be estimated according to:

- Stage at diagnosis (localised /metastatic),
- Receiving at least one targeted therapy during the data-collection period at any time of the study (yes/no),

- A 1st targeted therapy as line 1 or 2 vs a 1st targeted therapy as line 3 or more at any time of the study,
- Patients having undergone at least one surgery at any time of the study (yes/no).

These analyses will also consider the baseline date as the date of starting treatment at inclusion.

In addition, overall survival will be estimated in metasynchronous patients based on:

- Receiving at least one targeted therapy at any time of the study (yes/no),
- A 1st targeted therapy as line 1 or 2 vs a 1st targeted therapy as line 3 or more.

These two analyses will be duplicated using as the baseline date the date of starting treatment at inclusion, firstly, and the date of diagnosis, secondly.

Overall survival will also be estimated based on the main treatment line by differentiating between the main treatments (baseline date is the start date of each line). Therefore, patients may appear as many times as they have changed their main treatment.

Only the lines at inclusion and subsequently will be considered in the calculation, as the information collected for previous lines is not sufficient to be counted. Overall survival will not be shown if the start date of the main treatment is later than the date of the last visit. Patients still alive when they have completed the line will be censored on the start date of the next line or on the date of receiving the most recent news.

These overall survival analyses will be performed using the method described for analysis of overall survival for the main analysis, the baseline date of which is the date when treatment is started (See above). Analyses will be performed for all patients: a Kaplan-Meier estimator of the survival function for left-truncated and right-censored data will be computed using the SAS PROC PHREG procedure on SAS® software.

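### Additional PFS and OS subgroups in SAP 5.9.7 and 5.9.8 are defined by treatment that can start after inclusion, so some PFS curves can differ with no true effect; the OS bias has no predictable direction

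*SAP*

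**What the plan says.** SAP 5.9.7 estimates PFS on the treatment received at inclusion in many subgroups. Several are not fixed at entry:

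- "At least one targeted therapy at any time (yes/no", with related splits by number of targeted therapies and by line of the first one;
- "At least one surgery at any time of the study (yes/no";
- for chemotherapy patients, "Based on the total number of main treatment lines over the entire follow-up", cut at two. SAP 5.9.6 makes clear that the entire follow-up includes the prospective phase.

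Two further tables, one by extent of liver disease and one by count of metastatic sites, restrict the cohort in these words: "Progression-free survival will also be estimated overall for patients receiving targeted therapy at any time of the study based on".

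SAP 5.9.8 groups OS in the same way, from diagnosis and again from the start of the inclusion treatment. One split is "Receiving at least one targeted therapy during the data-collection period at any time of the study (yes/no". Another concerns the place of targeted therapy in the sequence of lines: "A 1st targeted therapy as line 1 or 2 vs a 1st targeted therapy as line 3 or more at any time". Surgery is handled likewise, with the group defined as "Patients having undergone at least one surgery at any time of the study (yes/no".

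Both sections name the same method: Kaplan-Meier with delayed entry, each patient in one fixed group. No landmark or time-dependent grouping is given. SAP section 6 discusses left truncation, loss to follow-up and confounding by treatment choice, but not this problem.

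Other subgroups in the same lists are known at entry and are sound in this respect: targeted therapy before inclusion, Ki67, stage at diagnosis, line number at inclusion and treatment at inclusion.

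**The concern.** SAP 5.5.1 counts a PFS event only while the patient is on the inclusion treatment, and otherwise censors at the last assessment on it. A later main line therefore starts after that PFS time is over, and the outcome helps to decide the group. SAP 5.5.1 also states that progression leads to a change of treatment.

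Take a chemotherapy patient included on line 2. If the treatment keeps working, the patient stays in the group with at most two lines. If it fails and another line follows, the patient moves to the group with more than two. The second group collects failures by construction.

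Delayed entry removes survivor time before inclusion only. It does nothing about the interval from inclusion to a later treatment.

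The affected contrasts concern targeted therapy, its place in the sequence, and surgery. The study answers a health authority that asked about sunitinib and everolimus relative to other treatments (Protocol, Justification for the study), so a reader could take such a gap as a finding.

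**Working it through.** **The plan's own figure.** The half-width of the 95% interval at the median is 1.96 × √(0.5²/n). For n = 150 it is 1.96 × √(0.25/150) = 0.080, and for n = 75 it is 1.96 × √(0.25/75) = 0.113. Both match SAP 4.2. The SAP gives no figure for these additional subgroups.

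**Null model.** Neither line number nor treatment affects progression or death.

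- From the documents: 24 months of follow-up after inclusion; delayed-entry Kaplan-Meier, S(t) = ∏(1 − d/Y); median OS of 38 months (a general pNET figure in the Protocol introduction).
- Assumed: median time to progression 11 months, a rate of ln 2/11 = 0.063 per month; later lines 8, 6 and 5 months; lines 1 to 4 at inclusion 40/30/20/10%; 85% start a further line after one ends, on average 1 month later; half the patients prevalent, entering at 0 to 12 months.
- The death rate is h before progression and r × h after it, with h solved to give the 38-month median.
- A share f of line endings other than death is not progression. PFS is then censored.

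**Total lines, at most two vs more than two, 12-month PFS**

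| f | r = 1 (true 0.38) | r = 5 (true 0.44) |
|---|---|---|
| 0% | 0.47 vs 0.31 | 0.57 vs 0.35 |
| 40% | 0.41 vs 0.35 | 0.51 vs 0.40 |
| 60% | 0.37 vs 0.38 | 0.46 vs 0.43 |

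At f = 60% a smaller gap remains at 24 months: 0.16 vs 0.13 (r = 1) to 0.24 vs 0.16 (r = 5). Grouped by line at inclusion, the two curves lie within 0.7 points of each other.

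A second model (median PFS 12 months, r = 3, 40% prevalent, f = 0) gives 24-month PFS of 0.329 vs 0.113 by total lines and 0.203 vs 0.205 by line at inclusion.

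**Targeted therapy ever vs never, 12-month PFS.** At f = 0 the range is 0.36 vs 0.41 to 0.39 vs 0.64. At f = 40% it is 0.375 vs 0.384 to 0.42 vs 0.54. At f = 60% it is 0.39 vs 0.33 to 0.43 vs 0.45. These inputs carry no share of patients treated before inclusion; such patients are already in the ever group at entry and dilute the gap. For two or more vs one targeted therapy, adding prior therapy narrows 0.22 vs 0.39 to 0.28 vs 0.40 (r = 1, f = 0).

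**Level shift, not separation.**

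- Second-line type (table 14.2.2.6.3): 0.336–0.340 vs 0.347–0.349, against a true 0.377. In the second model the curves coincide at 24 months (0.138 vs 0.137), below the whole cohort at 0.204.
- Cohort of tables 14.2.2.6.17 and .18: 0.34–0.36 where the true value is 0.38.

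**Surgery, 12-month PFS, yes vs no (r = 1).** 0.404–0.430 vs 0.340–0.361 if surgery is done while progression-free; 0.367–0.369 vs 0.381–0.389 if done at progression.

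**OS, targeted therapy ever vs never, 24 months.** A patient must survive to start a later treatment, which favours the ever group. Late starters are mostly progressors, which counts against it.

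| r | Ever | Never |
|---|---|---|
| 1 | 0.67–0.70 | 0.49–0.61 |
| 3 | 0.70–0.71 | 0.64–0.68 |
| 5 | 0.69–0.71 | 0.69–0.71 |
| 8, immediate switching | 0.69–0.71 | 0.71–0.74 |

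In the second model the difference runs from +0.18 to −0.045 over r = 1 to 10.

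**The case against.** The strongest objection is that SAP 5.5.1 says progression leads to a change of treatment, not that a new line implies progression. SAP 4.7 ignores the reason for stopping when it counts lines, treats a restart after more than 3 months as a new line, turns an addition to a somatostatin analog into a new main line, and counts chemo-embolisation as a line during the study. The CRF (section 3.3, Table 5) offers adverse event, patient decision, cumulative dose, scheduled stop and optimum response as reasons. This stands. It bears most on chemotherapy patients, for whom planned stops are plausible, and it is why every PFS size above depends on f.

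The objection on stakes also largely stands. These are additional descriptive curves with no named test. Some of the gaps are smaller than the plan's 11-point half-width at 75 patients. Several inclusion-based counterparts and the line-start PFS are already planned. Protocol 8.3.2.1 and SAP 6.4 both call treatment comparisons inappropriate. That caution, however, concerns how treatment was chosen. It does not tell a reader that the groups were formed by what happened afterwards.

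A reader might infer that every listed PFS split separates falsely, or that immortal time makes targeted therapy look better on OS. The documents support neither. Table 14.2.2.6.3 and tables .17 and .18 show curves that are somewhat too low. The OS sign depends on how strongly death follows progression, which neither document gives.

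**Conclusion.** Wrong as written, and limited to additional descriptive analyses. Grouping by later treatment lets the PFS outcome help to choose the group, and the planned estimator does not repair that.

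For total lines, and for ever or multiple targeted therapies, the groups with more treatment look worse under no effect as long as most line changes follow progression. For total lines the false 12-month gap is about 16 to 22 points at f = 0 (0.47 − 0.31; 0.57 − 0.35), 6 to 11 points at f = 40% (0.41 − 0.35; 0.51 − 0.40), and near zero at f = 60%. All rates are assumptions, and the real share is not in the documents. Confidence is high for the PFS mechanism. It is lower for surgery and OS, where the direction is uncertain and the OS bias may be about zero.

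Tables and figures concerned: 14.2.2.6.2, .6, .7, .9, .10, .13, .16 and .20; .3, .17 and .18 for level only; and 14.2.2.7.5 to .7 and .9 to .15. Primary PFS and OS group by treatment at inclusion and are not affected.

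**What to change.** 1. Define these subgroups by status known at inclusion: targeted therapy before or at inclusion, line of the first targeted therapy among those who have had one by then, surgery before inclusion, and line number at inclusion. SAP 5.9.3 already derives targeted therapy and surgery by period, and 5.9.7 already lists line number at inclusion.
2. For PFS by later exposure or total lines, rely on the line-start PFS already planned in 5.9.7. If a table is kept, label it as conditioned on later treatment and not for comparison.
3. Add this bias to SAP section 6, with reference to table 14.2.2.8.1, which shows how many patients stop their main treatment after progression.
4. Do not offer line-start OS as a cure, because "Patients still alive when they have completed the line will be censored on the start date of the next line". Nor do unadjusted time-dependent OS curves solve it: with no true effect, treating targeted therapy as time-varying gives a death-rate ratio of 0.99–1.01 when death is unrelated to progression, but 1.17–2.01 when the risk rises after progression.

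The cost is SAP wording and reprogramming of a set of additional tables, with no new data. Some listed tables disappear or have smaller yes groups.
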